## LIST OF ABBREVIATIONS

ADR	adverse drug reaction
AE	adverse event
AED	antiepileptic drug
BRV	brivaracetam
CDMS	clinical data management system
CGIC	Clinical Global Impression of Change
CI	confidence interval
CRO	contract research organization
DDD	Defined Daily Dose
eCRF	electronic Case Report form
FAS	Full Analysis Set
IEC	Independent Ethics Committee
IRB	Institutional Review Board
LEV	levetiracetam
MedDRA ®	Medical Dictionary for Regulatory Activities
NIS	noninterventional study
PGIC	Patient's Global Impression of Change
POS	partial-onset seizure(s)
PS	Patient Safety
QoL	quality of life
QOLIE-31-P	Patient Weighted Quality of Life in Epilepsy Inventory-Form 31
SAP	Statistical Analysis Plan
SmPC	Summary of Product Characteristics
SS	Safety Set

## 1 BACKGROUND AND RATIONALE FOR THE STUDY

In the European Union, Briviact® (Nubriveo® in Italy) (brivaracetam [BRV]) has been approved for adjunctive therapy in the treatment of partial-onset seizures (POS) with or without secondary generalization in patients 4 years of age and older with epilepsy. Three formulations have been developed for commercial use: film-coated tablets for oral administration (10, 25, 50, 75, and 100mg), an oral solution (10mg/mL), and a solution for intravenous injection (10mg/mL). Brivaracetam film-coated tablets, oral solution, and solution for intravenous injection show the same area under the concentration-time curve, while the maximum plasma concentration is slightly higher after intravenous administration.

Brivaracetam ((2S)-2-[(4R)-2-oxo-4-propyltetrahydro-1H-pyrrol-1-yl]butanamide) is a 2-pyrrolidone derivative and displays a high and selective interaction with a brain-specific binding site, synaptic vesicle protein 2A. This binding site appears to be the major target for its pharmacological activity.

Brivaracetam is rapidly and completely absorbed throughout the gastrointestinal tract. The extent of BRV absorption is not affected by food. The pharmacokinetics are dose-proportional from 10mg to 600mg. Brivaracetam is weakly bound to plasma proteins ( $\leq 20\%$ ). The volume of distribution is 0.5L/kg, a value that is close to that of total body water. The plasma half-life of BRV is approximately 9 hours; the total plasma clearance in patients was estimated to 3.6L/hour. The main metabolic pathway of BRV is by hydrolysis of the acetamide group by amidase to the corresponding carboxylic acid, while a second pathway is the  $\omega 1$ -hydroxylation mediated by CYP2C19. The combination of these 2 pathways results in the hydroxyacid metabolite. These 3 metabolites are not pharmacologically active. There is no evidence of chiral inversion of BRV. Brivaracetam is eliminated primarily by oxidative metabolism and by excretion in the urine. More than 95% of the dose, including metabolites, is excreted in urine within 72 hours after dosing; less than 10% of BRV is excreted unchanged in urine.

The efficacy of BRV for the adjunctive therapy of POS was established in 3 Phase 3 randomized, double-blind, placebo-controlled, fixed-dose, multicenter studies in subjects 16 years of age and older. The daily dose of BRV ranged from 5 to 200mg/day across these studies. All studies had an 8-week Baseline period followed by a 12-week treatment period with no up-titration. A total of 1558 patients received study drug, of which 1099 received BRV. Study enrollment criteria required that patients had uncontrolled POS despite treatment with either 1 or 2 concomitant antiepileptic drugs (AEDs). Patients were required to have at least 8 POS events during the Baseline period. Adjunctive BRV administration at doses of 50mg/day to 200mg/day without titration resulted in statistically significant and clinically relevant reductions in seizure frequency, including seizure freedom. Brivaracetam was effective and well tolerated when started at these therapeutic doses. Low incidences of adverse events (AEs) and low study discontinuation rates due to AEs were also observed with BRV. A recent small, open-label, Phase 3 study evaluating nonpsychotic behavioral AEs in patients receiving levetiracetam (LEV) who switched to BRV showed that, at the end of the 12-week treatment period, 93.1% patients (27/29) who switched to BRV had clinically meaningful reductions in behavioral AEs, which suggest that patients experiencing behavioral AEs associated with LEV may benefit from switching to BRV (Yates et al, 2015).

EP0077 is the first postauthorization observational study of BRV in the real world, and is designed to collect information on the effectiveness in patients with POS who are treated with BRV in clinical practice after the product is marketed in the European Union.

EP0077 is a postmarketing, multinational, multicenter, noninterventional study (NIS) conducted at specialized sites in approximately 10 European countries, with a 12-month Observation Period. Patients will be treated according to usual medical diagnostic procedures and therapy; commercially available BRV will be prescribed according to normal clinical practice and the current Summary of Product Characteristics (SmPC) in Europe for BRV. The prescription of BRV is clearly separated from the decision to include the patient in the study. No additional diagnostic or monitoring procedures are applied to the patients.

The primary objective of this study is to evaluate the effectiveness of BRV by determining the retention over a 12-month period in a real world setting. The secondary objective of this study is to assess seizure control with BRV treatment.

The patient (or legal representative) will be required to provide written data consent for the use of his/her medical data before inclusion in the study.

## **2 STUDY TYPE**

EP0077 is a postmarketing, multinational, multicenter NIS.

## **3 STUDY OBJECTIVES**

### **3.1 Primary objective**

The primary study objective is to evaluate the effectiveness of BRV in patients with epilepsy with POS with or without secondary generalization in daily clinical practice.

### **3.2 Secondary objective**

The secondary objective is to evaluate seizure control with BRV treatment.

## **4 STUDY VARIABLES**

### **4.1 Primary variable**

The primary variable is the BRV retention at 12 months (end of Observation Period).

Note: This variable is used as a measure of effectiveness.

### **4.2 Secondary variables**

The following secondary variables will be measured:

- BRV retention at 3 months
- BRV retention at 6 months
- Absolute reduction in POS frequency (seizures per 28 days) from Baseline to 3 months
- Absolute reduction in POS frequency (seizures per 28 days) from Baseline to 6 months
- Absolute reduction in POS frequency (seizures per 28 days) from Baseline to 12 months

- Absolute reduction in POS frequency (seizures per 28 days) from Baseline to end of Observation Period
- Percent reduction in POS frequency (seizures per 28 days) from Baseline to 3 months
- Percent reduction in POS frequency (seizures per 28 days) from Baseline to 6 months
- Percent reduction in POS frequency (seizures per 28 days) from Baseline to 12 months
- Percent reduction in POS frequency (seizures per 28 days) from Baseline to end of Observation Period
- Response based on percent reduction in POS (seizures per 28 days) at 3 months (response is a reduction of  $\geq 50\%$ )
- Response based on percent reduction in POS (seizures per 28 days) at 6 months (response is a reduction of  $\geq 50\%$ )
- Response based on percent reduction in POS (seizures per 28 days) at 12 months (response is a reduction of  $\geq 50\%$ )
- Response based on percent reduction in POS (seizures per 28 days) at end of Observation Period (response is a reduction of  $\geq 50\%$ )
- Seizure freedom at 3 months
- Seizure freedom at 6 months
- Seizure freedom at 12 months
- Seizure freedom at end of Observation Period
- Time to first seizure after first dose of BRV

#### 4.3 Other variables

The following other variables will be measured:

- Patient Weighted Quality of Life in Epilepsy Inventory-Form 31 (QOLIE-31-P) total and subscale scores at 3, 6, and 12 months and end of Observation Period, and change in QOLIE-31-P scores from Baseline to 3, 6, and 12 months and end of Observation Period
- Presence of clinically meaningful change from Baseline to 3, 6, and 12 months and end of Observation Period in QOLIE-31-P
- EpiTrack® performance at 6 and 12 months
- EpiTrack change category from Baseline to 6 and 12 months and from 6 months to 12 months
- EpiTrack total score at 6 and 12 months and change from Baseline to 6 and 12 months
- EpiTrack total and individual subtest scores at 12 months and change in EpiTrack scores from Baseline to 12 months
- Clinical Global Impression of Change (CGIC) rating at 3, 6, and 12 months and end of Observation Period

- Patient's Global Impression of Change (PGIC) rating at 3, 6, and 12 months and end of Observation Period
- Change in drug load (ie, number of products, daily dose per given product, ratio of dose and Defined Daily Dose [DDD, [http://www.whocc.no/atc\\_ddd\\_index/](http://www.whocc.no/atc_ddd_index/)], frequency, drug class) of AEDs from Baseline to 12 months and end of Observation Period

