### 12.2.3 Analysis of other variables

The following variables will be summarized using descriptive statistics:

- QOLIE-31-P: 7 multi-item subscales, health status item, and total score showing observed results and the change from Visit 1 (Baseline) to Visit 2 (Month 3), Visit 3 (Month 6), Visit 4 (Month 12), and Visit 4 (Month 12 and end of Observation Period)
- Total EpiTrack score and the individual scores of the 6 subtests showing observed results and the change from Visit 1 (Baseline) to Visit 3 (Month 6) and Visit 4 (Month 12)
- Change in drug load of AEDs from Visit 1 (Baseline) to Visit 4 (Month 12) and Visit 4 (Month 12 and end of Observation Period)

The following variables will be summarized using number and percentage:

- Patients with a clinically meaningful change in QOLIE-31-P from Baseline (improvement, no change, or worsening, based on the minimally important change; Borghs et al, 2012) to Visit 2 (Month 3), Visit 3 (Month 6), Visit 4 (Month 12), and Visit 4 (Month 12 and end of Observation Period)
- Patients in each of the cognitive performance categories using the EpiTrack tool (excellent, average, mildly impaired, or significantly impaired) at Visit 1 (Baseline), Visit 3 (Month 6), and Visit 4 (Month 12)

- Patients in change categories of cognitive function (improved, unchanged, or worsened) between the visits (from Visit 1 [Baseline] to Visit 3 [Month 6] and to Visit 4 [Month 12] and from Visit 3 [Month 6] to Visit 4 [Month 12]) based on the assessments using the EpiTrack tool
- Patients with each CGIC and PGIC rating at Visit 2 (Month 3), Visit 3 (Month 6), Visit 4 (Month 12), and Visit 4 (Month 12 and end of the Observation Period)
- Patients who improved, had no change, and worsened in CGIC and PGIC

These analyses will be performed on the FAS and may be repeated on the modified FAS.

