### **8.3.4 Change in drug load of AEDs**

Drug load of AEDs will be calculated at first BRV administration, Visit 4 (Month 12), and Visit 4 (Month 12/Withdrawal). Drug load of AEDs will include all concomitant AEDs and LEV (recorded separately in the CRF), in addition to BRV dosing.

Only AEDs (recorded as an AED, as LEV, or as BRV dosing) that are being taken on the date of the visit will be included in the calculations. Partial dates will be imputed as described in [Section 4.2.2](#) to ensure the inclusion of any medications which have the potential to have been taken on the date of the visit.

Drug load per AED at the visit is calculated as: daily dose (mg) / DDD, where DDD for each AED is defined in [Section 12.3](#) and daily dose for each AED is calculated as follows:

1. Convert the dose per intake into mg using the unit recorded for each AED in the CRF (ie, 1g = 1000mg)
2. Using the frequency of dose recorded, multiply the dose per intake in mg by the values shown in [Table 8-4](#).

Table 8-4: Daily dose calculation		
Frequency	Description	Multiply dose per intake by:
QD	Once daily	1
BID	Twice daily	2
TID	3 times daily	3
QID	4 times daily	4
5XD	5 times daily	5
6XD	6 times daily	6
QOD	Every other day	1/2
QAM	Every morning	1
QPM	Every evening	1
QS	Every week	1/7
Q2S	Every 2 weeks	1/14
BIS	Twice per week	2/7
TIS	3 times per week	3/7
QM	Every month	1/28
BIM	Twice per month	2/28
TIM	3 times per month	3/28
Q2M	Every 2 months	1/56
Q3M	Every 3 months	1/84
PRN	As needed	Excluded from calculation

The drug load per AED at each visit will be added together to give a total AED drug load per visit. To avoid an underestimation of the drug load on the first and last visits (on which only 1 of the usual 2 doses may have been recorded), AED drug load at first BRV administration will be

calculated for the Day 2 for all patients and the last available record with morning and evening dosage will be used for the Visit 4 drug load analysis.

All drug load analyses will be performed on the FAS and the modified FAS.

The total AED drug load at first BRV administration (Baseline), Visit 4 (Month 12), and Visit 4 (Month 12/Withdrawal), and the change from Baseline will be summarized by descriptive statistics. Change from Baseline is defined as: Total AED drug load at Visit 4 (Month 12) or Visit 4 (Month 12/Withdrawal) – total AED drug load at first BRV administration (Baseline).

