The number of AEDs (including LEV, VNS use and BRV) taken per patient at first BRV administration (Baseline), Visit 4 (Month 12), and Visit 4 (Month 12/Withdrawal), and change from Baseline will be summarized by descriptive statistics. The number of AEDs at first BRV administration (Baseline) will be equal to the number of AEDs at Study Entry as described in [Section 6.4](#). Patients with VNS use at first BRV administration (Baseline) will be considered to have VNS use during the entire study and as such it will be counted as an AED at Visit 4 (Month 12) and Visit 4 (Month 12/Withdrawal) as appropriate. The total number of AEDs at a visit is a count of the number of concomitant AEDs, LEV, or BRV that are being taken on the date of the visit with partial dates imputed as described in Section 4.2.2, plus any VNS use. Change from Baseline is defined as: Total number of AEDs at Visit 4 (Month 12) or Visit 4 (Month 12/Withdrawal) – total number of AEDs at first BRV administration (Baseline).

A by-patient listing of drug load data will be provided on the All Subjects Documented set. The listing will include the total drug load, number of AEDs (including LEV and BRV) taken per patient, the changes from Baseline, AEDs taken (including LEV or BRV), the daily dose per given product, DDD, drug load per AED, and frequency at each visit.

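### Change in AED drug load is summarized only with BRV included, so the change in concomitant AEDs cannot be read from any planned table

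*Protocol*

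**What the plan says.** Protocol 4.3 names "Change in drug load (ie, number of products, daily dose per given product, ratio of dose and Defined Daily Dose" and goes on to frequency and drug class. It does not say whether BRV belongs in the load. Protocol 12.2.3 asks for descriptive statistics of "Change in drug load of AEDs from Visit 1 (Baseline) to Visit 4 (Month 12") and again with the end of the Observation Period included.

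SAP 8.3.4 settles the content: "Drug load of AEDs will include all concomitant AEDs and LEV (recorded separately in the CRF), in addition to BRV dosing". It then aggregates: "The drug load per AED at each visit will be added together to give a total AED drug load per visit". Descriptive statistics are planned for that total and for its change, which is "Total AED drug load at Visit 4 (Month 12) or Visit 4 (Month 12/Withdrawal) – total AED drug load at first BRV administration (Baseline"). The only other drug-load summary is a count: "The number of AEDs (including LEV, VNS use and BRV) taken per patient at first BRV administration (Baseline") and at both versions of Visit 4. The components, namely "the daily dose per given product, DDD, drug load per AED, and frequency at each visit", appear in a by-patient listing and not in a table.

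Two rules decide what counts at Visit 4. One restricts the calculation to AEDs "that are being taken on the date of the visit will be included in the calculations". The other, placed after the daily-dose table in the same section, takes the most recent record that shows both a morning and an evening dose.

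For the count, SAP 8.3.4 sets Baseline equal to the number of AEDs at study entry from SAP 6.4, where the categories run 0, 1, 2, 3 and >3.

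**The concern.** BRV is prescribed here as adjunctive therapy, and protocol 8.2 leaves physicians free to add or withdraw any medication. Protocol section 15 accepts that changes in concomitant AEDs may affect the results and says that their possible impact will be evaluated. Drug load is the planned summary of how AED treatment changes from Baseline to Visit 4, so it is the natural place to look for that evaluation.

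The planned change mixes two movements that can go in opposite directions: the dose of the study drug and the load of everything else. A reader who sees a mean change near zero cannot tell stable background treatment from a falling background load offset by rising BRV. What is at stake is any statement in the study report about concomitant AED load. No effectiveness or safety endpoint depends on it.

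**Working it through.** The documents give no target, precision or expected value for drug load, so there is no planned figure to reproduce. The check applies the SAP formula to illustrative patients.

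**Inputs.** DDDs from SAP Table 12-1: BRV 100, LEV 1500, lacosamide 300 mg/day. BRV doses of 50 and 200 mg/day are the limits named in SAP 3.5 and serve only as arithmetic inputs. The patients are assumptions.

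**Formula.** Load = sum over AEDs of daily dose / DDD. Change in total = change in BRV load + change in non-BRV load. Any AED held constant cancels.

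**BRV increased (applies to both Visit 4 summaries)**

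| Illustrative patient | BRV change | Non-BRV change | Reported total |
|---|---|---|---|
| BRV 50 to 200, LEV 1500 stopped after Baseline | (200-50)/100 = +1.5 | (0-1500)/1500 = -1.0 | +0.5 |
| BRV 100 to 200, LEV 1500 stopped after Baseline | (200-100)/100 = +1.0 | -1.0 | 0.0 |
| BRV 50 to 200, nothing else changed | +1.5 | 0.0 | +1.5 |

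The first row reverses the sign of the concomitant change, the second hides it, and the third reports an increase where no concomitant AED moved.

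For group means, mean total change = mean BRV change + mean non-BRV change. The sign of a fall in non-BRV load is lost whenever the mean BRV rise is larger. Neither mean is planned as a summary. Medians and quartiles do not add, so they cannot be separated at all.

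**BRV stopped (mainly Month 12/Withdrawal).** Under protocol 8.2, permanently stopping BRV leads to withdrawal, and the Month 12 summary is restricted to completers. The last-record column assumes that the BRV dose did not change between Day 2 and the last full record.

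| Illustrative patient | Total, date-of-visit rule | Total, last-record rule | Non-BRV change |
|---|---|---|---|
| BRV 100 stopped, nothing else changed | -1.0 | 0.0 | 0.0 |
| BRV 100 stopped, lacosamide 300 added | -1.0 + 1.0 = 0.0 | +1.0 | +1.0 |
| BRV 200 stopped, lacosamide 300 added | -2.0 + 1.0 = -1.0 | +1.0 | +1.0 |

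Under the date-of-visit rule, if a share f of patients in that column has stopped BRV from d DDD, the mean total falls by f × d with no change in other AEDs. For assumed f of 20% to 50% and d of 1.0 to 2.0, that is 0.2 × 1.0 = 0.2 up to 0.5 × 2.0 = 1.0 DDD. Under the last-record rule with a constant dose it is 0.

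**Count.** If BRV is counted on the day of its first dose, the 0 category at study entry cannot be filled. This suggests that the study-entry count leaves BRV out, against the statement in SAP 8.3.4 that BRV is in.

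| Illustrative patient, still on BRV | Baseline includes BRV | Baseline omits BRV |
|---|---|---|
| One other AED throughout | 2 to 2 = 0 | 1 to 2 = +1 |
| Two other AEDs, one stopped | 3 to 2 = -1 | 2 to 2 = 0 |

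In the second patient the true change in concomitant AEDs is -1, and the right-hand reading conceals it.

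**The case against.** The strongest answer is that nothing is wrong with the variable. Protocol 4.3 speaks of the drug load of AEDs, BRV is an AED, and a total that includes it is a legitimate measure of overall treatment burden. Neither study objective asks whether BRV spares other AEDs. This stands: the total should stay, and the documents do not support calling it the wrong variable or giving a non-BRV figure precedence over it.

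A second answer is that other tables help. SAP 10.1 tabulates BRV dose categories from Day 2 to Day 330, which shows the direction of BRV dosing. However, it does so on the Safety Set and modified FAS, at fixed days and not at the withdrawal visit, and in bands such as 100 to <150 mg, which is 0.5 DDD wide. SAP 6.4 tabulates concomitant AEDs by class and preferred term, but for any use during dosing, with no Baseline-to-Visit 4 comparison. If BRV is counted at both times, it cancels from the Month 12 count for patients still on it. That is a fair point, but it depends on the unclear Baseline definition, and a count does not register dose changes.

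A reader might infer that stopping BRV definitely lowers the withdrawal column. The documents do not establish this, because the last-record rule can carry the final full BRV dose forward. A reader might also infer that the SAP made an undeclared cut that belonged in SAP 3.9. That is weak: protocol 12.2.3 asks only for descriptive statistics of the change, and most components are listed. Only change by drug class has no place in the drug-load outputs.

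Finally, the patients are invented, and the documents give no mean BRV or non-BRV change. That also stands. The examples show what the summary can hide and do not predict what it will hide.

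**Conclusion.** The point holds as a gap in reporting. As planned, change in drug load is BRV change plus concomitant change, and no table gives the concomitant part. Within the 50 to 200 mg/day range in SAP 3.5, a BRV dose change can move the total by up to 1.5 DDD in either direction. Stopping another AED taken at its DDD moves it by 1.0, so offset or reversal is arithmetically possible. Whether it occurs in the group mean depends on dosing data that the documents do not contain.

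Two inconsistencies within SAP 8.3.4 go with it and must be reconciled: the date-of-visit rule against the last-record rule for stopped BRV, and a Baseline count said to include BRV but equated with a study-entry count that admits 0 AEDs. The first could shift an individual result by 0.5 to 2.0 DDD (BRV 50 to 200 mg/day over a DDD of 100). The second could add 1 to every otherwise unchanged retained patient.

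This is an other variable in a descriptive study. The primary and secondary results do not depend on it.

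**What to change.** In SAP 8.3.4:

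- Keep the total load. Beside it, summarize BRV load and the load of all AEDs other than BRV (LEV included) at Baseline, Visit 4 (Month 12) and Visit 4 (Month 12/Withdrawal), each with change from Baseline.
- Give the number of AEDs excluding BRV at the same times, with change. For the count that includes BRV, state whether BRV is counted at Baseline, and align this with SAP 6.4.
- State one counting rule for BRV that has been stopped by Visit 4, so that the date-of-visit and last-record sentences no longer conflict. Footnote that rule on the Month 12/Withdrawal table.

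The cost is SAP wording and a few extra table rows. The load per AED is already derived for the listing, so no new data are needed. A further table of class and daily dose per product is not needed to close this gap.
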